5.9.2 SURGICAL PROCEDURE

The surgical procedure is described in the system Surgical Technique (**Appendix A**). The Operative CRF shall be completed.

In case of an adverse event, the appropriate CRF should be filled.

5.9.3 **POSTOPERATIVE MANAGEMENT**

In general, postoperative management shall be conducted according to the description in the CRFs.

Immediate post-operative management should be as per routine hospital standard of care.

Prior to *discharge*, the following examinations/tests shall be performed (refer also to **Table 8** below and to the description in the Discharge CRF):

- Physical examination
- > Neurological Examination
- ➢ X-Ray evaluation

The results of the said examinations shall be recorded on the Discharge CRF.

In addition, the patient shall be interviewed regarding adverse events; in case of an adverse event, the appropriate form should be filled.

The patients shall be instructed to refrain from the use of NSAIDS for three months postoperatively.

During *follow-up visits*, the following post-operative examinations/tests shall be performed (refer also to **Table 8** below and to the description in the post-operative CRFs):

- Physical examination
- > Neurological Examination
- X-Ray evaluation

The results of the said examinations shall be recorded.

At every follow-up visits the following forms shall be completed (refer to **Table 9**):

- Post-operative CRF
- Patient follow-up questionnaires (VAS (pain), ODI, SF-12, VAS (donor site pain, if applicable), and VAS (satisfaction))

In addition, the patient shall be interviewed at each follow-up visit regarding adverse events, and the appropriate form should be filled. If a non-scheduled postoperative visit results from such an event, it should be noted on the form.

Table 8 below lists the assessment schedule and examinations.

CARBOCLEAR PEDICLE SCREW SYSTEM

Table 8: Assessment Schedule

Description	Pre- Procedure	Operation	Discharge	6 Weeks Visit	3 Months Visit	6 Months Visit	12 Months Visit	24 Months Visit	Annual Visit [§]	Unscheduled Visit
	Trocedure			V ISIL	v 151t	V ISIL	V ISIL	V ISIL	VISIL	VISIL
Inclusion/Exclusion Criteria	\checkmark									
Informed Consent (signed & dated)										
Demographic & Medical History										
Physical Examination	\checkmark		\checkmark	\checkmark	\checkmark	\checkmark	\checkmark	\checkmark	\checkmark	\checkmark
Neurological Examination					\checkmark					
X-Rays (AP, Lateral and Flexion/Extension)		Fluoroscopy	$\sqrt{*}$	$\sqrt{*}$	$\sqrt{*}$				\checkmark	√ **
Patient Questionnaires (VAS (Pain), ODI, SF-12, VAS (Satisfaction))	$\sqrt{\alpha}$				\checkmark	\checkmark	\checkmark	\checkmark	\checkmark	
CT Scan						¥	\sqrt{F}	\sqrt{F}	$\sqrt{2}$	
AE Recording			\checkmark	\checkmark	\checkmark	\checkmark			\checkmark	

[§] Will be performed after the 24-month follow-up, until the last patient completes 2-year follow-up.
* Except for flexion/extension X-rays.
** Will be performed only if required according to the physician discretion.

¤ Except for patient satisfaction VAS.

CT scan will be conducted for patients in whom bridging bone status cannot be determined in X-Rays. ¥

Table 9 below lists the Questionnaires and Forms that need to be completed during baseline and postoperatively evaluations.

CARBOCLEAR PEDICLE SCREW SYSTEM

Table 9: Forms/Questionnaires to be Completed at Pre-Op. and Follow-Up Visits

Form Type	Pre- Operation	Operation	Discharge	6 weeks Post-Op.	3 Months Post-Op.	6 Months Post-Op.	12 Months Post-Op.	24 Months Post-Op.	Annual Visit *	Unscheduled Visit
Pre-Op. CRF										
(Enrollment and	\checkmark									
Baseline Forms)										
Operative CRF		\checkmark								
Discharge CRF										
Post-Op. CRF				\checkmark	\checkmark	\checkmark	\checkmark	\checkmark		
Unscheduled Visit										2
CRF										N
Medications CRF –				Medicat	tions Form sh	ould be comp	leted at discha	rge and follow-	-up sessions,	
Follow Up			in case	any concorr	nitant medicat	tion was used	during hospita	lization or sinc	e last visit, re	spectively
Adverse Event CRFs										
(AEs, SAE,						When appl	licable			
Additional Surgery)										
Protocol Deviation						When appl				
Conclusion CRF						At 24 Months	s, or when appl	icable		
VAS (Pain),					2	2	2	2	\checkmark	
ODI & SF-12	N			N	N	N	N	N	N	
VAS (Donor Site				\checkmark	2	N	V	V		
Pain), if applicable				N	v	Ň	N	N	N	
VAS (Satisfaction)									\checkmark	

* Will be performed annually after reaching the 24-month follow-up, until the last patient completes 2-year follow-up

Subjects who shall withdraw from the study will have the Conclusion CRF completed for them upon their request to withdraw from the study. The reason for withdrawal and any alternative treatment suggested to the patient shall be indicated on the form. In case a subject who is lost to follow up returns at a later stage, this will be indicated as a remark on the Conclusion CRF along with the reason the patient missed the previous follow-up session(s).

5.10 EVALUATION OF PRIMARY OUTCOME MEASURES

5.10.1 FUSION EVALUATION

Fusion will be evaluated radiographically, by A-P, lateral and flexion/extension X-Rays (flexion/extension films will be used for the assessment of angular and translational motions). As detailed below, in case of inconclusive findings regarding bridging bone, a CT scan will also be performed, and evaluated by the core lab.

Fusion assessment shall be made postoperatively, starting at 6 months and at each follow-up session afterwards.

Each fusion area (between the endplates, at right posterolateral, and at left posterolateral, as applicable) will be assessed separately.

All radiographs will be read by two independent, board-certified, radiologists from Medical Metrics, Inc., with experience in musculoskeletal imaging, blinded to clinical outcomes, and without any financial interest in CarboFix Orthopedics, to ensure consistent reading of the radiographs and elimination of bias. In the case of a disagreement between the two radiographic assessors, a third independent reviewer will evaluate the radiographic images to adjudicate the findings.

Please refer to **Appendix D** for radiographic protocols, including Image Acquisition Protocol, Image Transfer Protocol, and Radiographic Evaluation Protocol. All said protocols were provided to CarboFix by Medical Metrics, Inc.

Fusion Radiographic Patient Success is defined when all the following radiographic endpoints are met at 24 months:

- a. Angular motion < 3°; AND
- b. Translational motion < 3 mm; AND
- c. Presence of continuous bridging bone between the involved motion segment, *i.e.*:
 - Presence of interbody (between endplates) bridging bone and absence of radiolucency > 50%; OR
 - Presence of left posterolateral bridging bone; OR
 - Presence of left posterolateral bridging bone.

Regarding angular motion, reporting of subjects will be provided in the following three groups:

- 1. those with $\leq 3^{\circ}$ total angular motion,
- 2. those between 3° and 5° of motion, and
- 3. those with $\geq 5^{\circ}$ of motion.

In case bone graft would be placed in the interbody space as well as posterolaterally, on both sides, bridging would be assessed in each of the three areas. Bridging in any one area would be considered adequate to document the presence of affirmative bridging.

Radiolucency will be evaluated as the percent coverage of radiolucent lines along the graft / endplate interface. There will be a single assessment for the superior and inferior bone / graft interfaces combined. Radiolucency will be evaluated primarily from lateral views. The view (neutral, flexion or extension) showing the most severe extent of radiolucency will be used to document the assessment.

Radiolucency will be used to document bone resorption. Particularly in the early stages of healing, poor conformance of the graft with the endplate geometry, *i.e.* poor "fit and fill", will not be identified as radiolucency.

Radiolucency will be graded in accordance with the following definitions:

None: No radiolucent lines along the interbody graft / endplate interface.

Mild: $\leq 25\%$ radiolucent lines along the interbody graft / endplate interface.

Moderate: 26% - 50% radiolucent lines along the interbody graft / endplate interface.

Severe: > 50% radiolucent lines along the interbody graft / endplate interface.

Non-fusion will be indicated in the following cases:

Angular motion $\ge 3^\circ$ OR translational motion ≥ 3 mm OR absence of continuous bridging bone, *i.e.*:

- Absence of interbody bridging bone and presence of radiolucency >50%; AND
- Absence of left posterolateral bridging bone; AND
- Absence of right posterolateral bridging bone.

Possibly fusion: Patients in whom the status of bridging bone is inconclusive will undergo fine cut CT scan to determine bridging bone and fusion status. At each timepoint, starting at 6 months, any inconclusive X-Rays assessment relates to bridging bone shall be repeated within window, using CT.

Information regarding the CT scans (including the procedures for obtaining and transmitting the CT scans) is presented in the Radiographic Protocol (**Appendix D**). Definition of bridging bone evaluated in CT scan is as follows (on top of motion evaluated by flexion/extension X-Rays):

Presence of continuous bridging bone between the endplates; or between the right facets, pedicle and/or transverse processes; or between the left facets, pedicle and/or transverse processes, as applicable.

The fusion rate obtained in the study shall be compared to the fusion rates reported in the literature (as summarized in **Section 5.2.1**).

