5.1.1 OUTCOME MEASURES

The following outcome measures will be evaluated in subjects participating in the study: Primary Effectiveness and Safety Outcome Measures:

- Fusion: evaluated radiographically (by AP, lateral and flexion/extension X-Rays) at 24 months; fusion is defined as:
 - a. Angular motion $< 3^{\circ}$ ¹⁶; AND
 - b. Translational motion < 3 mm; AND
 - c. Presence of continuous bridging bone between the involved motion segment ¹⁷, *i.e.*:
 - Presence of interbody (between endplates) bridging bone and absence of radiolucency > 50%; OR
 - Presence of left posterolateral ¹⁸ bridging bone; OR
 - Presence of left posterolateral ¹⁸ bridging bone.

¹⁶ In addition to angular motion of 3 degrees, the Company will provide fusion data and analysis using a threshold of 5° of angular motion. Additional information is provided in **Section 3.10.1**.

¹⁷ The definition above calls for "continuous" bridging bone (with or without trabeculation). That is, solid bridging with no intervening fractures or discontinuities. Conventional plain film imaging rarely supports visualization of trabeculae.

¹⁸ Right posterolateral - between the right facets, pedicle and/or transverse processes; left posterolateral - between the left facets, pedicle and/or transverse processes.

- Pain (low back and/or leg/s): assessed based on Visual Analogue Scale (VAS), at 24 months; defined as an improvement of at least 20 mm on a 100 mm VAS from the baseline level.
- Function: assessed by Oswestry Disability Index (ODI), at 24 months; defined as an improvement of at least 15 points from the baseline level.
- Safety:
 - No worsening in neurological status (motor, sensory, reflex, straight leg raising, and tenderness assessments) and no new permanent neurological deficits present for at least 2 successive visits at or beyond 6 months (out to 24 months);
 - Absence of device-related serious adverse events through 24 months.
 - Absence of subsequent surgical interventions at the index level through 24 months.

Secondary Outcome Measures:

- Subject's Overall Well-Being: assessed by 12-Item Short Form Health Survey (SF-12), at 24 months;
- Satisfaction: assessed based on VAS, at 24 months;
- > **Donor Site Pain**: assessed based on VAS, at 24 months;
- Operation time;
- **Blood loss**.

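### The fusion criterion in the primary endpoint lists the left side twice and omits the right, and the non-fusion definition is not its complement

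*Combined protocol and SAP*

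**What the plan says.** The fusion success criterion is set out four times: in the synopsis (Section 2), Section 5.1.1, Section 5.10.1 and Section 5.12. Each time it requires angular motion below 3°, translational motion below 3 mm, and bridging bone by any one of three alternatives. The first alternative is interbody bridging without radiolucency above 50%. The second and third both read "Presence of left posterolateral bridging bone". Section 5.12 repeats the bullets in full within the composite primary endpoint and does not refer back to Section 5.10.1.

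Other text names both sides:

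- Footnote 18 in Section 5.1.1, whose marker sits on both duplicated bullets, defines "Right posterolateral - between the right facets, pedicle and/or transverse processes" and then the left equivalent.
- Section 5.10.1 states: "Each fusion area (between the endplates, at right posterolateral, and at left posterolateral, as applicable) will be assessed separately".
- Section 5.10.1 adds, for graft placed in the interbody space and posterolaterally on both sides: "Bridging in any one area would be considered adequate to document the presence of affirmative bridging".

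For non-fusion, Section 5.10.1 requires motion at or above either limit, or "absence of continuous bridging bone". It then spells out that last phrase in three bullets joined by AND: "Absence of interbody bridging bone and presence of radiolucency >50" per cent; absence of left bridging; and "Absence of right posterolateral bridging bone". A further category, possible fusion, covers only patients whose bridging status is inconclusive; they go to CT. The CT definition of bridging is "Presence of continuous bridging bone between the endplates; or between the right facets, pedicle and/or transverse processes", or the corresponding left-sided structures. It has no radiolucency term.

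**The concern.** These bullets define one component of the composite primary endpoint and the separate fusion criterion. Three things go wrong if they are followed as printed.

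1. **Side.** Right posterolateral bridging never counts towards success. No statement of the success bullets is correct, so there is none to fall back on, and someone programming the composite from Section 5.12 alone sees only the left.
2. **Non-fusion.** The definition is narrower than the opposite of fusion. A plain non-union, with no bridging at any site and radiolucency of 50% or less, does not meet the bullets. Fused and non-fused counts then need not add up to the number of conclusive readings.
3. **Radiolucency.** The any-one-area sentence and the CT definition drop the radiolucency condition. Interbody bridging alone with radiolucency above 50% can therefore be read as fused or not fused.

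**Working it through.** **The plan's own figure.** The only precision statement for fusion is in Section 5.12: 88% with a 95% interval of ±6.4% for 100 patients, lower bound 81.6%. It reproduces: 1.96 × √(0.88 × 0.12 / 100) = 0.0637, and 0.88 − 0.0637 = 0.8163. The problem here is classification, so this calculation is not in dispute.

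**Inputs.** Take both motion criteria as met and let four yes/no findings vary: interbody bridging (I), radiolucency above 50% (R), left bridging (L) and right bridging (T). That gives 2⁴ = 16 patterns.

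- Success as written: (I and not R) or L or L.
- Success with the right restored: (I and not R) or L or T.
- Non-fusion as written: (not I and R) and not L and not T.
- Complement of corrected success: (not I or R) and not L and not T.

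**Success count.** As written, L present gives 8 patterns; L absent with I present and R absent adds 2, for a total of 10. With the right restored, L or T present gives 12, and I present with R, L and T all absent adds 1, for a total of 13. The 3 patterns that change all have T present, L absent and the interbody alternative unmet.

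**Non-fusion count.** As written, only one pattern qualifies (I, L and T absent, R present). With OR in place of AND, three qualify.

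| Patterns (fused / non-fused / neither) | As written | Right restored | Both corrected |
|---|---|---|---|
| All 16 | 10 / 1 / 5 | 13 / 1 / 2 | 13 / 3 / 0 |
| Interbody graft only (L and T absent; 4 patterns) | 1 / 1 / 2 | 1 / 1 / 2 | 1 / 3 / 0 |
| Posterolateral graft only (I absent, R not gradable; 4 patterns) | 2 / 0 / 2 | 3 / 0 / 1 | 3 / 1 / 0 |

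**Patterns that are neither.** As written, the five are:

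1. no bridging anywhere, radiolucency 50% or less;
2. interbody bridging only, radiolucency above 50%;
3. right bridging only, radiolucency 50% or less;
4. right bridging only, radiolucency above 50%;
5. right and interbody bridging, no left, radiolucency above 50%.

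Patterns 3 to 5 come from the missing right side. Patterns 1 and 2 come from the AND and remain after the side is corrected.

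**Any-one-area and CT wording.** Bridging defined as I or L or T is present in 14 of the 16 patterns. It differs from the corrected criterion (13) at one pattern only: interbody bridging alone with radiolucency above 50%.

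**Who is exposed.** In the IDE patients posterolateral fusion is optional (Section 5.2), so the interbody-only row applies to some of them, and there restoring the right changes nothing. The roughly 45 patients added from the ongoing OUS study had posterolateral fusion only (Section 5.13.1). Radiolucency is graded along the interbody graft/endplate interface, so they would have nothing to grade as above 50%. Scored with these bullets, none of them could be called non-fused on bridging.

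**Illustration, with assumed counts.** If 1, 2, 5 or 10 of 100 patients moved from success to failure, a rate of 88% would become 87%, 86%, 83% or 78%, with lower bounds of 80.4%, 79.2%, 75.6% and 69.9% by the same formula. The protocol does not say which count, if any, is realistic.

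**The case against.** The left/left wording is evidently a slip, and the protocol largely shows how to read it: one footnote on both bullets defines both sides, each side is assessed separately, and the non-fusion and CT definitions name the right. A sensible reader would not fail a patient for right-sided bridging. The core laboratory also works from its own radiographic evaluation protocol (Appendix D), which is not in the text available and may be correct. The non-fusion gap does not touch the success count, because success is defined positively and no specified analysis uses the non-fused count. The lead-in to the non-fusion bullets also covers plain non-union in ordinary language. The OUS exposure is conditional: Section 5.13.1 says the same assessment tools are used, but Section 5.14.2 reports OUS fusion by a rule that names no side.

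Most of this stands as a limit on consequence. It does not remove the defect. The any-one-area sentence is conditioned on graft in all three areas, so on its terms it does not cover other graft patterns. The bullets that spell out absent bridging are narrower than the phrase they explain. The possible-fusion category does not fill the gap, because it is for inconclusive readings only.

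**Conclusion.** The point holds and should be corrected. The success criterion is wrong as printed in all four places, including the composite primary endpoint, although the intended reading is clear. Restoring the right side reclassifies 3 of 16 patterns from not fused to fused. The non-fusion definition is a separate logical error: it leaves 2 of 16 patterns unclassified even after the side is fixed, and it affects the non-fusion label, not the success numerator. The radiolucency question after CT concerns one pattern.

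The counts assume both motion criteria are met and weight all patterns equally, so they measure gaps in the rule and not numbers of patients. No effect on the fusion rate, the composite rate or the study conclusion has been shown, and none can be estimated from the documents.

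**What to change.** - In the synopsis and Sections 5.1.1, 5.10.1 and 5.12, change the second left posterolateral bullet to right.
- In Section 5.10.1, define non-fusion as any conclusive reading that does not meet the fusion definition. In the interbody bullet, replace AND with OR before the radiolucency condition.
- Add a sentence that the interbody alternative counts as not met where no interbody graft was placed. This goes slightly further than the existing as-applicable wording, so it should be stated outright.
- Reconcile the any-one-area sentence and the CT definition with the bridging criterion, stating whether the radiolucency condition still applies after CT.
- Check that the radiographic evaluation protocol in Appendix D uses the same definitions.

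The cost is one word in four places, one connective and a few clarifying sentences, with no new data or analyses. Because the text defines an endpoint, the change falls outside the notification-only route in Section 5.19.5 and should be handled as a protocol amendment.

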5.10.2 PAIN AND FUNCTION EVALUATION

Pain and functionality will be assessed using dedicated questionnaires.

VAS (*Back, Right Leg, and Left Leg Pain*): The assessment of pre- and postoperative pain shall be performed using scores determined from measurements of responses to pain question for each location (*i.e.*, low back, right leg, and left leg), provided on a 100 mm Visual Analog Scale (VAS). The anchor points are "No Pain" (0 mm) and "Severe Pain" (100 mm). Patients will be instructed to draw a single line across the scale at the point that best described their level of pain.

The pain VAS assessment will be administered preoperatively as well as at each postoperative visit, starting at 6 weeks.

ODI (*Functionality*): The Oswestry Disability Index (ODI) will be used to assess function. The ODI questionnaire is based on patient's responses to ten questions, which focus on pain intensity, personal care, lifting, walking, sitting, standing, sleeping, sex life, social life, and traveling. Each question has six possible answers. The responses to each question ranges from zero to five points. A lower numeric score represents a better pain and disability status regarding that variable (0 points for functionality with no associated pain or no extra pain; 5 points for inability to perform function due to pain). A total ODI score is determined by adding the scores of the individual questions and dividing that total by the maximum possible total score (50 if all questions are answered); this yields a percentage. Therefore, ODI scores shall be presented ranging from 0% to 100%, with a lower percentage indicating less pain and disability.

The ODI questionnaire will be administered preoperatively as well as at each postoperative visit, starting at 6 weeks visit.

Clinically Meaningful Improvements -

• Individual patient clinically meaningful improvement with respect to *pain* is defined as postoperative improvement at 24 months of at least 20 mm on a 100 mm VAS from the baseline level. Data regarding pain improvement will be provided for all pain components (*i.e.*, low back, right leg and left leg). The

above improvement criterion of 20/100 mm refers to the dominant pain component for each patient. For example: if the preoperative VAS (pain) for a given patient was 90 (low back), 60 (right leg), and 40 (left leg), improvement of at least 20 mm will be required for the back pain component. Improvement in both legs, though, will be also reported.

• Individual patient clinically meaningful improvement with respect to *functionality* is defined as postoperative improvement at 24 months of at least 15 points on the ODI graded on a 100-point scale as compared to baseline assessment.

It is noted, that the indicated improvement values in pain and function are regarded clinically meaningful and were used in other, IDE studies for similar devices.

Average improvement and standard deviation for VAS (pain) and ODI, as well as the proportion of patients that met the success criterion for VAS and ODI, will be reported. The VAS and ODI results obtained in the study shall be also compared to VAS and ODI results reported in the literature (as summarized in Section 5.2.1).

